1. OBJECTIVES

1.1. Primary Objective

To estimate the objective response rate (ORR) using immune RECIST (iRECIST) in patients with metastatic pancreatic cancer treated with plerixafor and cemiplimab.

1.2. Secondary Objectives

- 1.2.1. To estimate ORR using RECIST v.1.1.
- 1.2.2. To assess safety and characterize toxicities of plerixafor in combination with cemiplimab.

1.3. Exploratory Objectives

- 1.3.1. To assess progression free survival (PFS), time to progression (TTP), disease control rate (DCR), best overall response (BOR), duration of response (DOR), duration of clinical benefit (DCB), and time to objective response (TTOR) using, iRECIST and RECIST v.1.1.
- 1.3.2. To assess the overall survival (OS).
- 1.3.3. To measure pharmacokinetic and pharmacodynamic parameters in pancreatic cancer patients treated with plerixafor and cemiplimab including but not limited to increase numbers of CD34+ cells in the blood.
- 1.3.4. To collect pre- and on-treatment biopsies to explore the association of features of the tumor microenvironment in response to therapy, including but not limited to assessment of:
 - T cell subset markers (CD4, CD8, FoxP3, Granzyme A/B, CD69), immune regulation (PD-L1, PD-L2, CTLA4, LAG-3, IDO1, TIM-3), and immune cell population markers (NK, DC, B cell, MDSC, etc.). Techniques used for analyses may include but are not limited to immunohistochemistry (IHC) and mass cytometry.
 - Transcriptomics using single-cell RNASeq analysis. Immune cell numbers and activation state will be characterized.
 - CXCR4 and CXCL12 IHC
- 1.3.5. To evaluate molecular determinants of response using next generation sequencing and other sequencing techniques.
- 1.3.6. To collect peripheral blood mononuclear cells (PBMC) and serum to identify potential therapeutic targets, biomarkers and predictors of response (OS, PFS and best overall response).

- Measure pre- and post-treatment changes in PBMCs including effector, helper, and regulatory T cells, NK cells, monocytes, and macrophages through cell phenotyping analysis and gene expression profiling.
- Proteomic approaches will be used on pre- and post-treatment sera to identify targets and biomarkers of response or toxicity.

1.3.7. To evaluate clonal T cell populations in the tumor and in the periphery through T cell receptor sequencing, and to functionally assess mutation associated neoantigen-specific T cells.

1.3.8. To measure serum and salivary cortisol levels and correlate with response and immune cell infiltration.

1.3.9. To use CT imaging for body composition analyses and correlate with outcomes.

1.3.10. To measure changes in cfDNA content and quantity in response to therapy.

1.4. Study Design

This is a single center, phase II trial in patients with previously-treated metastatic pancreatic cancer. There will be a safety run-in (n=6). Plerixafor will be administered at 80 mcg/kg/hr x 24 hours per day x 7 days each cycle. The cycle will be repeated every three weeks. Cemiplimab will be administered on day 1 of each cycle at a dose of 350mg by intravenous infusion. Tumor biopsies will be obtained at baseline and on either Cycle 1 Day 8 or Cycle 2 Day 1 for alternating patients. An optional biopsy may be obtained at the time of disease progression.

The primary endpoint is objective response rate (irORR: CR + PR) per iRECIST. The treatment regimen would be considered of insufficient activity for further study in this population if the irORR is 7.7% or less, and the minimum required level of efficacy that would warrant further study is an irORR of 20%. The sample size is calculated to detect an improved irORR from 7.7%[1] to 20%. A modified Simon's two-stage design is planned. A total of 21 patients will be entered in the first stage. If ≤ 1 subject responds, the treatment will be terminated and we will conclude the regimen is ineffective. If ≥ 2 subjects respond, then additional 18 patients will be enrolled. If a total of 5 or fewer subjects respond in stage one and two combined, we consider the regimen ineffective. If a total of 6 or more respond, we conclude the regimen is promising and warrant further study. The maximum sample size will be 39.

The study will consist of a pre-screening period, a screening period (within 28 days of the first dose), a treatment period, and a follow-up period. Subjects will receive treatment on 21 day cycles, and will come to clinic for dosing and/or assessments on Day 1 of each cycle and additional days for safety and immune monitoring follow up as per the study schedule in **Section 9**. No dose escalations or reductions of plerixafor or cemiplimab are allowed. Complete information on study drug administration, schedule, and dosing can be found in **Section 4.1**.

The study will include a safety run-in for the first six patients. If more than 1 of the first 6 patients experiences an unacceptable toxicity within the first cycle, then enrollment will be halted and the overall risk-benefit ratio of the study will be reconsidered. At any time thereafter, if more than 33% of patients are observed to experience unacceptable toxicity within the first cycle, enrollment will be halted and the safety of the combination will be re-evaluated. Complete unacceptable toxicity criteria can be found in **Section 4.7**.

Treatment may continue up to a maximum of 2 years, or until discontinuation due to toxicity, lack of clinical benefit as determined by the investigator, subject withdrawal, or termination of the study. Subjects may continue on treatment with radiographic disease progression if subject is clinically stable and investigator believes the treatment is providing benefit. Criteria for removal from treatment are found in **Section 4.10**.

Tumor biopsies, PBMC, serum and plasma collection, and computed tomography (CT) scans or magnetic resonance imaging (MRI), if CT is contraindicated, will be obtained at baseline and during treatment for clinical assessments and correlative analyses. Tumor assessments will be made using RECIST 1.1/iRECIST.

Subjects will return to the study site 30 (+/- 7) days after the final administration of study treatment for an end of treatment (EOT) evaluation. Subjects will be considered in the treatment period until 30 days after the last dose of study drug. After completion of treatment and EOT assessments, all subjects will continue to be followed per **Section 4.12**.

Information on progression-free survival and overall survival may continue to be gathered for supplementary analyses after the completion of the primary analysis.

2. BACKGROUND

2.1. Study Disease

Despite decades of basic and clinical research, effective therapy for the treatment of patients with pancreatic ductal adenocarcinoma (PAC) remains one of the greatest unmet clinical needs in oncology today. Currently, PAC accounts for approximately 7% of all cancer-related mortality and has the lowest 5-year survival rate among all cancer types in the United States. PAC is currently the 4th leading cause of death from cancer in the U.S. with estimates in 2016 for 53,070 people diagnosed and about 41,780 dying from the disease [2]. Worldwide it will claim more than 300,000 lives this year [3]. It is projected that by 2030, pancreatic cancer will become the second leading cause of cancer-related death in the US [4].

Most patients are initially diagnosed with advanced disease that is inoperable with median survival of less than 1 year. Patients with advanced disease are usually treated with chemotherapy, with the intent of prolonging survival and palliating symptoms (pain, weight loss and decrease in performance status). From 1997, gemcitabine was the standard chemotherapy for advanced pancreatic cancer after demonstrating a significant improvement in survival compared to 5-fluorouracil (5-FU) [5]. Median survival was 5.65 months for gemcitabine-treated patients and

4.41 months for 5-FU treated patients, while overall tumor response rates were 5.4% and 0%, respectively.

Until recently, only erlotinib, an oral epidermal growth factor (EGF) inhibitor, was shown in a Phase 3 study to modestly improve median OS in combination with gemcitabine over gemcitabine alone (6.24 months for the doublet versus 5.91 months for gemcitabine alone) without a significant difference in ORR between the treatments [6]. In 2011, a Phase 2/3 trial conducted by a French consortium study group demonstrated FOLFIRINOX, a combined regimen of oxaliplatin, irinotecan, fluorouracil, and leucovorin significantly increased survival in patients with pancreatic cancer over gemcitabine alone. Median OS was 11.1 months versus 6.8 months for each treatment, respectively (hazard ratio [HR] for death, 0.57; 95% confidence interval [CI], 0.45 to 0.73; $p < 0.001$). The ORR was also increased to 31.6% from 9.4% ($p < 0.001$). Adverse events were increased in the FOLFIRINOX group and 5.4% of patients in this group experienced febrile neutropenia [7]. Although FOLFIRINOX represents an efficacious regimen in pancreatic cancer, there are still concerns about its potential toxicity and it is being reserved for the most fit patients.

In the MPACT (Metastatic Pancreatic Adenocarcinoma Clinical Trial) study, *nab*-paclitaxel combined with gemcitabine demonstrated a statistically significant and clinically meaningful median OS of 8.5 versus 6.7 months (HR 0.72, $p < 0.0001$ including a 59% increase in one-year survival (35% versus 22%, $p=0.0002$) and demonstrated double the rate of survival at two years (9% versus 4%, $p=0.02$) as compared to gemcitabine alone in previously untreated patients with metastatic pancreatic cancer. *nab*-/gemcitabine also demonstrated a statistically significant improvement in key secondary endpoints compared to gemcitabine alone, including a 31% reduction in the risk of progression or death with a median PFS of 5.5 versus 3.7 months (HR 0.69, $p < 0.0001$) and an ORR of 23% compared to 7% (response rate ratio of 3.19, $p < 0.0001$)[8]. The MPACT study and regimen formed the basis for full FDA approval in September 2013 for the first-line treatment of metastatic adenocarcinoma of the pancreas.

Nanoliposomal irinotecan in combination with 5-FU was recently approved for patients with previously treated pancreatic cancer. However, it is unknown if this combination is better than 5-FU and irinotecan (FOLFIRI) as 5-FU was the comparator and there was no benefit in patients who previously received irinotecan so the value of this drug is questionable in FOLFIRINOX treated patients[1, 9]. Therapies for patients with metastatic pancreatic cancer are urgently needed.

Novel approaches, such as immunotherapy, hold promise in this very difficult cancer.

2.2. Dual Blockade of PD-1 and CXCR4

A large rectangular area of the page is completely blacked out with a solid black rectangle, obscuring several paragraphs of text. This redaction is positioned below the section header and spans most of the page width.

[figure not shown]
2.3. Dose Selection

[figure not shown]
2.3.1. Cemiplimab

Cemiplimab is a PD-1 receptor blocking antibody. The initial US approval was in September 2018 for the treatment of patients with metastatic or locally advanced cutaneous squamous cell carcinoma who are not candidates for curative surgery or curative radiation. The recommended dosage is 350mg as an intravenous infusion over 30 minutes every 3 weeks and is therefore, the dose and schedule selected for this study.

2.3.2. Plerixafor

2.4. Rationale

This study aims to combine plerixafor and cemiplimab to synergistically improve T cell activation, proliferation, and infiltration to combat immune evasion by tumors. This study will be an open label, phase II study to evaluate ORR using iRECIST in patients with metastatic previously-treated pancreatic adenocarcinoma.

3. PATIENT SELECTION

3.1. Eligibility Criteria

3.1.1. Age \geq 18 years.

3.1.2. ECOG performance status of 0-1 (**Appendix A**).

3.1.3. Have histologically- or cytologically-proven ductal adenocarcinoma of the pancreas.

- 3.1.4. Have metastatic disease.
- 3.1.5. Have documented radiographic disease progression at the time of study enrollment, after previous systemic chemotherapy given in a neoadjuvant, adjuvant, locally advanced or metastatic setting.
- 3.1.6. Presence of at least one lesion with measurable disease as defined by 10 mm in longest diameter for a soft tissue lesions or 15 mm in short axis for a lymph node by RECIST 1.1.
- 3.1.7. Patient's acceptance to have a tumor biopsy of an accessible lesion at baseline and on treatment.
- 3.1.8. Life expectancy of greater than 3 months.

- 3.1.9. Adequate organ and marrow function as defined below:

- Leukocytes $\geq 3,000/\text{mcL}$
- Absolute neutrophil count $\geq 1,000/\text{mcL}$
- Platelets $\geq 90 \times 10^3/\text{uL}$
- Hemoglobin $\geq 8.0 \text{ g/dL}$
- Total bilirubin ≤ 1.5 upper limit of normal (ULN) except subjects with Gilbert Syndrome, who can have total bilirubin $< 3.0 \text{ mg/dL}$
- AST(SGOT) and ALT(SGPT) $\leq 3.0 \times \text{ULN}$
- Alkaline phosphatase $\leq 5.0 \times \text{ULN}$
- Creatinine $\leq 1.5 \times \text{ULN}$ or creatinine clearance (CrCl) $\geq 40 \text{ mL/min}$ (if using the Cockcroft-Gault formula below):

$$\text{Female CrCl} = \frac{(140 - \text{age in years}) \times \text{weight in kg} \times 0.85}{72 \times \text{serum creatinine in mg/dL}}$$

$$\text{Male CrCl} = \frac{(140 - \text{age in years}) \times \text{weight in kg} \times 1.00}{72 \times \text{serum creatinine in mg/dL}}$$

- Albumin $\geq 3.0 \text{ g/dL}$

- 3.1.10. Women of childbearing potential (WOCBP) must have a negative serum pregnancy test (minimum sensitivity 25 IU/L or equivalent units of human chorionic gonadotropin [HCG]). WOCBP is defined in **Section 4.8**. NOTE: If a patient has a positive or indeterminate serum or urine pregnancy test, then an ultrasound must be done to rule out pregnancy to enroll on trial.

- WOCBP must agree to follow instructions for method(s) of contraception from the time of enrollment for the duration of treatment with study drug(s) plus 5 half-lives of study drug(s) plus 4 weeks (duration of ovulatory cycle) for a total of 5 months post treatment completion.
- Men who are sexually active with WOCBP must agree to follow instructions for method(s) of contraception for the duration of treatment with study drug(s) plus 5 half-lives of study drug(s) plus 90 days (duration of sperm turnover) for a total of 7 months post-treatment completion.
- At least one barrier method of contraception must be employed by all sexually active patients (male and female), regardless of other methods, to prevent the transfer of body fluids.

3.1.11. Ability to understand and willingness to sign a written informed consent document.

3.2. Exclusion Criteria

- 3.2.1. Patient has a known history or evidence of brain metastases.
- 3.2.2. Patient who has had chemotherapy, radiation, or biological cancer therapy within 14 days prior to the first dose of study drug.
- 3.2.3. Patient has received an investigational agent or used an investigational device within 28 days of the first dose of study drug.
- 3.2.4. Patient is expected to require any other form of systemic or localized antineoplastic therapy while on study.
- 3.2.5. Patients who have had surgery within 28 days of dosing of investigational agent, excluding minor procedures (dental work, skin biopsy, etc.), celiac plexus block, and biliary stent placement.
- 3.2.6. Patients who have received any prophylactic vaccine within 14 days of first dose of study drug or received a live vaccine within 30 days of planned start of study therapy.
- 3.2.7. Patients with a history of prior treatment with an anti-CXCR4 agent.
- 3.2.8. Currently using any chronic systemic steroids (at doses exceeding 10 mg daily of prednisone equivalent) or any other form of immunosuppressive therapy (steroid premedication for contrast is allowed).
- 3.2.9. Patients receiving growth factors including, but not limited to, granulocyte-colony stimulating factor (G-CSF), GM-CSF, erythropoietin, within 14 days of study drug administration. Use of such agents while on study is also prohibited.

- 3.2.10. History of severe hypersensitivity reaction to any monoclonal antibody. Exceptions may be approved by Protocol Chair if the patient has subsequently tolerated an antibody.
- 3.2.11. Evidence of clinical or radiographic ascites. Trace or small amounts of radiographic ascites may be approved by the Protocol Chair.
- 3.2.12. History of clinically significant and/or malignant pleural effusion.
- 3.2.13. Uncontrolled intercurrent illness including, but not limited to, ongoing or active infection, symptomatic congestive heart failure, unstable angina pectoris, symptomatic cardiac arrhythmia, or psychiatric illness/social situations that would limit compliance with study requirements.
- 3.2.14. Subjects with active autoimmune disease. Subjects with Graves or Hashimoto's disease, vitiligo, type I diabetes mellitus, psoriasis or other conditions not requiring systemic treatment, or conditions not expected to recur in the absence of an external trigger are permitted to enroll. Subjects with autoimmune conditions requiring systemic treatment in the past may be approved by the Protocol Chair.
- 3.2.15. Presence of any tissue or organ allograft, regardless of need for immunosuppression, including corneal allograft. Exceptions can be approved by the Protocol Chair if loss of the graft is not a clinical concern. Patients with a history of allogeneic hematopoietic stem cell transplant will be excluded.
- 3.2.16. All toxicities attributed to prior anti-cancer therapy other than alopecia and fatigue must have resolved to grade 1 (National Cancer Institute Common Terminology Criteria for Adverse Events [CTCAE], version 5) or baseline before administration of study drug. Subjects with toxicities attributed to prior anti-cancer therapy which are not expected to resolve and result in long-lasting sequelae, such as neuropathy after chemotherapy, are permitted to enroll.
- 3.2.17. Have received a diagnosis of human immunodeficiency virus (HIV), hepatitis B (Hep B sAg negative permitted) or hepatitis C (patients who are hepatitis C antibody positive may be enrolled if they are confirmed with negative viral load at screening)
- 3.2.18. Patient has a pulse oximetry of <92% on room air.
- 3.2.19. Patient is on supplemental home oxygen.
- 3.2.20. Patient has clinically significant heart disease (such as uncontrolled angina, myocardial infarction within the last 3 months or congestive heart failure of New York Heart Association III or IV).

3.2.21. Patient is, at the time of signing informed consent, a regular user (including “recreational use”) of any illicit drugs or other substance abuse (including alcohol) that could potentially interfere with adherence to study procedures or requirements.

3.2.22. Patient is unwilling or unable to follow the study schedule for any reason.

3.2.23. Patient is pregnant or breastfeeding.

3.2.24. Have rapidly progressing disease, as judged by the investigator (e.g., rapid progression through prior treatment[s]).

3.2.25. History of significant, recurrent, unexplained postural hypotension in the last 6 months.

3.3. Inclusion of Women and Minorities

Both men and women of all races and ethnic groups are eligible for this trial.

4. TREATMENT PLAN

4.1. Agent Administration

Treatment will be administered on an outpatient basis. Appropriate dosing delays are described in **Section 5**. No investigational or commercial agents or therapies other than those described below in **Table 1** may be administered with the intent to treat the patient’s malignancy.

Table 1: Regimen Description

REGIMEN DESCRIPTION					
Agent	Premedications; Precautions	Dose	Route	Schedule	Cycle Length
Cemiplimab	No prophylactic pre-medication will be given unless indicated by previous experience in an individual subject per Section 4.2	350mg	IV infusion over 30 (+/-15) min*	Day 1	21 days
Plerixafor		80mcg/kg/hr (1920mcg/kg/24hrs)	Continuous IV infusion over 7 days**	Days 1-7	21 days

*Infusion times are approximate and may be adjusted based on subject tolerability.

** Plerixafor formulation for infusion is stable for 5 days at room temperature. Therefore, patients will return to clinic on day 4 to exchange the infusion bag and on day 8 to discontinue their plerixafor infusion. The bag exchange on Day 4 should occur within 1 hour of completion of the first infusion bag.

Subjects should be observed for a minimum of 30 minutes between the administration of cemiplimab and plerixafor.

Please see **Section 5.2** for guidance regarding dosing delays.

Antiemetic medications should not be routinely administered prior to dosing of drugs. See **Section 4.2.1** for subsequent premedication recommendations following an infusion reaction.

4.2. General Concomitant Medication and Supportive Care Guidelines

Cemiplimab and plerixafor can cause hypersensitivity reactions. Subjects should be closely monitored for potential AEs during infusion and potential AEs throughout the study.

4.2.1. Infusion Reactions

If an infusion reaction were to occur, it might manifest with fever, chills, rigors, headache, rash, pruritus, arthralgias, hypo- or hypertension, bronchospasm, or other allergic-like reactions. All grade 3 or 4 infusion reactions should be reported to the Protocol Chair and reported as an SAE if criteria are met. Infusion reactions should be graded according to CTCAE (version 5.0) guidelines.

Treatment recommendations are provided below and may be modified based on local treatment standards and guidelines as appropriate:

For grade 1 symptoms (mild reaction; infusion interruption not indicated; intervention not indicated):

Remain at bedside and monitor subject until recovery from symptoms. The following prophylactic premedications are recommended for future infusions: diphenhydramine 50 mg (or equivalent) and/or acetaminophen 325 to 1000 mg at least 30 minutes before additional co-administrations.

For grade 2 symptoms (moderate reaction requires therapy or infusion interruption but responds promptly to symptomatic treatment [e.g., antihistamines, non-steroidal anti-inflammatory drugs, narcotics, corticosteroids, bronchodilators, IV fluids]; prophylactic medications indicated for 24 hours):

Stop the infusion, begin an IV infusion of normal saline, and treat the subject with diphenhydramine 50 mg IV (or equivalent) and/or acetaminophen 325 to 1000 mg; remain at bedside and monitor subject until resolution of symptoms. Corticosteroid or bronchodilator therapy may also be administered as appropriate. If the infusion is interrupted, restart the infusion at 50% of the original infusion rate when symptoms resolve; if no further complications ensue after 30 minutes, the rate may be increased to 100% of the original infusion rate. Monitor subject closely. If symptoms recur then no further study drug will be administered at that visit. Administer diphenhydramine 50 mg IV, and remain at bedside and monitor the

subject until resolution of symptoms. The amount of study drug infused must be recorded on the case report form (CRF).

The following prophylactic premedications are recommended for future infusions: diphenhydramine 50 mg (or equivalent) and/or acetaminophen 325 to 1000 mg should be administered at least 30 minutes before study drug infusions. If necessary, corticosteroids (up to 25 mg of SoluCortef or equivalent) may be used.

For grade 3 or grade 4 symptoms (severe reaction, grade 3: prolonged [i.e., not rapidly responsive to symptomatic medication and/or brief interruption of infusion]; recurrence of symptoms following initial improvement; hospitalization indicated for other clinical sequelae [e.g., renal impairment, pulmonary infiltrates]; grade 4: (life threatening; pressor or ventilator support indicated):

Immediately discontinue infusion of study drug. Begin an IV infusion of normal saline, and treat the subject as follows: Recommend bronchodilators, epinephrine 0.2 to 1 mg of a 1:1,000 solution for subcutaneous administration or 0.1 to 0.25 mg of a 1:10,000 solution injected slowly for IV administration, and/or diphenhydramine 50 mg IV with methylprednisolone 100 mg IV (or equivalent), as needed. Subject should be monitored until the investigator is comfortable that the symptoms will not recur. All study drugs will be permanently discontinued. Investigators should follow their institutional guidelines for the treatment of anaphylaxis. Remain at bedside and monitor subject until recovery from symptoms.

In the case of late-occurring hypersensitivity symptoms (e.g., appearance of a localized or generalized pruritus within 1 week after treatment), symptomatic treatment may be given (e.g., oral antihistamine, or corticosteroids).

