4.7. Unacceptable Toxicity

Unacceptable toxicities are defined as any adverse event requiring permanent discontinuation per **Section 4.10.2** (exceptions for permanent discontinuation must be approved by the Protocol Chair).

If more than 1 of the first 6 patients experiences an unacceptable toxicity within the first cycle, then enrollment will be halted, and the overall risk-benefit ratio of the study will be reconsidered. At any time thereafter, if more than 33% of patients are observed to experience unacceptable toxicity within the first cycle, enrollment will be suspended until further review and consideration by the Protocol Chair. There will be no dose reductions for cemiplimab or plerixafor.

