4.10.2. Cemiplimab- and Plerixafor-Related Adverse Events

Permanent discontinuation of all study treatment should be considered for any of the following (exceptions for permanent discontinuation must be approved by the Protocol Chair):

1. Severe or life-threatening related AEs, including, but not limited to, any of the following (the Protocol Chair must be notified in the event of these AEs):
 - Any grade 2 treatment-related uveitis, eye pain, or blurred vision that does not respond to topical therapy and does not improve to \leq Grade 1 severity within the re-treatment period OR requires systemic treatment
 - Any grade 3 non-skin, drug-related AE lasting > 7 days, with the following exceptions:
 - Grade 3 treatment-related uveitis, pneumonitis, bronchospasm, neurologic toxicity, hypersensitivity reaction, or infusion reaction of any duration requires discontinuation
 - Grade 3 treatment-related endocrinopathies adequately controlled with only physiologic hormone replacement do not require discontinuation
 - Grade 3 treatment-related laboratory abnormalities do not require treatment discontinuation except:

- Grade 3 treatment-related thrombocytopenia > 7 days OR that is associated with bleeding requires discontinuation
 - Any treatment-related liver function test (LFT) abnormality that meets the following criteria require discontinuation:
 - ALT or AST $> 8 \times$ ULN, regardless of duration, or
 - ALT or AST $> 5 \times$ and $\leq 8 \times$ ULN, that fails to return to \leq Grade 1 within 2 weeks despite medical intervention, or
 - Total bilirubin $> 5 \times$ ULN, or
 - Potential drug-induced liver injury (DILI) event (**Section 6.5.5**)
- Any grade 4 treatment-related AE or laboratory abnormality, except for the following events which do not require discontinuation:
 - Grade 4 neutropenia ≤ 7 days
 - Grade 4 lymphopenia and leukopenia.
 - Isolated Grade 4 amylase or lipase abnormalities that are not associated with symptoms or clinical manifestations.
 - Isolated grade 4 electrolyte imbalances/abnormalities that are not associated with clinical sequelae and are corrected with supplementation/appropriate management within 72 hours of their onset.

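### Section 4.2.1 gives two conflicting instructions for an infusion reaction that resolves, is restarted and recurs, which leaves re-dosing and the Cycle 1 toxicity count unclear

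*Combined protocol and SAP*

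**What the plan says.** In Section 4.2.1 a grade 2 infusion reaction leads to stopping the infusion and treating the symptoms. Then: "If the infusion is interrupted, restart the infusion at 50% of the original infusion rate when symptoms resolve". If the reaction returns: "If symptoms recur then no further study drug will be administered at that visit". The grade 2 text closes with advice for later dosing: "The following prophylactic premedications are recommended for future infusions".

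The grade 3 or 4 text of the same section lists "recurrence of symptoms following initial improvement" among the features that make a reaction grade 3. Its instruction is "All study drugs will be permanently discontinued".

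Section 4.10.2 lists grade 3 reactions for which "hypersensitivity reaction, or infusion reaction of any duration requires discontinuation". Its lead-in speaks only of considering permanent discontinuation, and it allows exceptions approved by the Protocol Chair.

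Section 4.7 ties the safety count to 4.10.2: "Unacceptable toxicities are defined as any adverse event requiring permanent discontinuation". Sections 1.4, 4.7 and 12.2 halt enrollment if more than 1 of the first 6 patients has such a toxicity in Cycle 1, and later if more than 33% do.

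Section 6.2 records an adverse event that changes grade at its highest grade.

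**The concern.** Under the grade 2 text the infusion restarts only after symptoms have resolved. Any recurrence on that path therefore follows improvement, which is what the grade 3 definition describes. One event fits both texts. One text withholds drug for a visit and looks ahead to further infusions; the other ends treatment.

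Two things are at stake. The first is whether the patient is exposed again, which can arise in any cycle. The second is whether a Cycle 1 event is one that requires permanent discontinuation, and so enters the run-in rule and the 33% boundary. The event is foreseeable, since Section 4.2 notes that both drugs can cause hypersensitivity reactions.

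**Working it through.** **Step 1: the passages side by side, for a reaction that resolves, is restarted and recurs.**

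| Text | Handling of the recurrence | Later dosing |
|---|---|---|
| 4.2.1, grade 2 | No more drug at that visit | Foreseen: premedication advice for future infusions |
| 4.2.1, grade 3 definition | Recurrence after improvement is grade 3 | None: all study drugs stopped permanently |
| 4.10.2 | Grade 3 infusion reaction of any duration requires discontinuation | None, unless the Protocol Chair approves an exception |
| 6.2 | Recorded at the highest grade reached | Not addressed |

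Section 6.2 points to grade 3 on the case report form but does not settle re-dosing. A form showing grade 3 for a patient re-dosed under the grade 2 text is therefore possible.

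**Step 2: the plan's own operating characteristics.** The inputs are the 12.2 boundaries (2 events at 6 patients, 3 at 7–9, and so on up to 13 at 37–39), checked after each patient from the 6th. An exact binomial recursion gives these stop probabilities:

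- true risk 0.10: 13.0% (plan: 12.4%, from 5000 simulations)
- true risk 0.20: 44.4% (plan: 45.8%)
- true risk 0.30: 78.7% (plan: 78.7%)

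All the plan's stop percentages are reproduced to within 1.5 points. The table is not in error; what is unclear is whether this event feeds it.

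**Step 3: one patient in the run-in.** With exactly one other unacceptable toxicity among the first 6, leaving the event out gives 1/6 and enrollment continues. Counting it gives 2/6 and enrollment halts.

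**Step 4: illustration over a range of rates.** The documents give no rate for recurrent reactions. Assume a 10% risk of other unacceptable toxicity in Cycle 1. Assume also that a further share q of patients have a recurrent reaction in Cycle 1 and no other unacceptable toxicity, so that the risks add. With p = 0.10 + q,

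P(halt in run-in) = 1 − (1 − p)^6 − 6p(1 − p)^5.

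For q = 0: 1 − 0.5314 − 0.3543 = 0.114. For q = 0.10: 1 − 0.2621 − 0.3932 = 0.345 (0.3446 before rounding from the four-decimal terms).

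| q (assumed) | p | Run-in halt | Stop at any time, 12.2 rule |
|---|---|---|---|
| 0 (not counted) | 0.10 | 11.4% | 13.0% |
| 1% | 0.11 | 13.4% | 15.5% |
| 2% | 0.12 | 15.6% | 18.2% |
| 5% | 0.15 | 22.4% | 27.1% |
| 10% | 0.20 | 34.5% | 44.4% |

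**The case against.** The best defence is that the two texts can be read in sequence. Withholding drug at that visit is a bedside instruction; it does not say that drug is given next time, and it is compatible with permanent discontinuation afterwards. The premedication advice may be meant for grade 2 reactions that do not recur. Infusion reactions are to be graded by CTCAE 5.0, and the highest grade is recorded. Section 4.2.1 also describes its content as adaptable: "Treatment recommendations are provided below and may be modified based on local treatment standards and guidelines as appropriate".

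Much of this stands. It rules out the claim that the two instructions can never both be obeyed. It does not remove the conflict. If every recurrence became grade 3 with permanent discontinuation, limiting the instruction to that visit would serve no purpose. The protocol never says that the recurrence moves the patient to the next paragraph. Local modification and Protocol Chair exceptions both need a default to depart from, and here there are two.

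A reader might infer that the toxicity count simply follows whichever paragraph is used at the bedside. That goes too far: 4.7 runs through 4.10.2, which works by grade, and 6.2 favors grade 3. What remains open is whether a recurrence handled under the grade 2 text is one that requires permanent discontinuation.

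A reader might also infer that the choice changes response status. Under 10.1 and 12.1, a toxicity stop makes a patient a non-responder automatically only if it comes before any post-baseline assessment. The study calendar notes in Section 9 schedule an end-of-treatment CT 30 days (± 4 weeks) after the final dose. The effect is possible only if no post-baseline scan is obtained.

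**Conclusion.** The conflict within 4.2.1 is real and should be resolved. It leaves re-dosing unsettled in any cycle and, for Cycle 1 events, leaves it unclear whether the event is an unacceptable toxicity under 4.7 and 12.2.

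The firm statement of size is the single-patient one: with exactly one other event in the run-in, the classification decides whether enrollment continues or halts. The probabilities are illustrative. They rest on an assumed 10% base risk, an assumed 1% to 10% rate of recurrent reactions, and additive risks. At 1% or 2% the run-in halt probability rises by 2.0 or 4.2 points (13.4 − 11.4 and 15.6 − 11.4); only the upper end of the range gives a large shift. Confidence is high in the wording conflict, and lower in how often it would matter.

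**What to change.** Reconcile the grade 2 and grade 3 texts of 4.2.1, together with 4.10.2, so that a reaction that resolves, is restarted and recurs has one stated grading and one stated handling. Remove the sentence or clause that conflicts. Make the count in 4.7 follow that same grading; because 12.2 already refers to 4.7, a short cross-reference there is enough. Which handling is clinically right is for the sponsor and investigators to decide, and no view is taken here.

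The cost is a wording change in 4.2.1, alignment of 4.10.2 if needed, and cross-references in 4.7 and 12.2. No patients or procedures are added.
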